rTMS has been shown to improve declarative memory (Wang et al., 2014; Figure 1), but it is unknown whether this enhancement is associated with behavioral effects on procedural memory or whether modulation of the striatal network affects declarative memory. Although TMS has been used to show a double dissociation between stimulation of different cortical sites and their effects on procedural and declarative memory (Cohen & Robertson, 2011; Galea et al., 2010), these studies did not include a measure of target engagement. Therefore, these studies cannot be considered mechanistically informative. To optimize the effect of rTMS on learning and memory, a mechanistic understanding of how these improvements occur is required. We will attempt to fill this gap by using functional connectivity (FC) as a marker of target engagement, and measuring changes in procedural and declarative learning. Because understanding mechanistic changes are necessary to optimize the effect on behavior, changes in FC will serve as our primary outcome measure.

[figure not shown]

Figure 1. Results from Wang et al. (2014) demonstrating stimulus-dependent changes in associative memory. Panel A demonstrates the task used. Twenty face-name pairs were observed by participants during the study phase of the task. During the test phase, the faces were shown and the participant was asked to recall the corresponding word. Panel B indicates the results from baseline, after 3 days of stimulation, and 24 hours after the 5th day of stimulation for real and sham stimulation. Results are shown in proportion to baseline. \* -  $p < 0.05$ , \*\*- $p < 0.01$

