## 4. Study Design and Methods

### a. Study overview

This protocol will include four experiments, each using rTMS and MRI, in a between-subjects design (Table 1). Experiments 1 and 3 will use PPC rTMS. Experiments 2 and 4 will use M1 stimulation.

	Active Stimulation Type	Active Stimulation Site	Targeted Network
Experiment 1	Facilitatory (20-Hz)	PPC	Hippocampal
Experiment 2	Facilitatory (20-Hz)	M1	Striatal
Experiment 3	Inhibitory (cTBS or 1-Hz)	PPC	Hippocampal
Experiment 4	Inhibitory (cTBS or 1-Hz)	M1	Striatal

Table 1. Experiment Details. PPC = Posterior Parietal Cortex, M1 = Motor Cortex.

Table 2 shows the timeline of each experiment. Each study will include FC and memory testing at baseline, 24-hours after, and two weeks after three days of rTMS. The number of days of rTMS is based on pilot data where three days of stimulation produces significant enhancement of rsFC in the hippocampal network in five out of six individuals tested. Each participant will make a maximum of 6 visits to the lab (not including screening), for a maximum time commitment of 14 hours. The 24-hour follow-up will occur between 12 and 48 hours after the last stimulation session, and the 2-week follow-up will occur 14-21 days after baseline measurements. Scanning will occur in the NIH NMRF. All visits will be outpatient.

	Baseline Day	rTMS Sessions	Post Stimulation Day	2-week follow-up
Group 1	Baseline FC and Memory	Active Stimulation 3-sessions	FC and Memory Testing	FC and Memory Testing
Group 2	Baseline FC and Memory	Vertex Stimulation 3-sessions	FC and Memory Testing	FC and Memory Testing

Table 2. Timeline of each experiment.

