### iv. rTMS

The parietal target in Experiments 1 and 3 will be the region of the left PPC with the greatest connectivity with the left hippocampus derived from the baseline resting-state fMRI session, (similar to Wang et al. 2014). The left PPC was chosen because of its dense connections with the hippocampus (Cavada & Goldman-Racic, 1989; Mesulam et al., 1977).

The target in Experiments 2 and 4 will be the M1 area of maximal connectivity with the right striatum. M1 has extensive projections to the striatum (Parent & Hazrati, 1995), and these regions are functionally connected at rest (Di Martino et al., 2008).

rTMS targets will be marked in the participant's anatomical MRI volume and located with a frameless stereotaxic system. If any experiment, for any reason, fails to produce useful individual targets, a literature-based location for the parietal cortex (Wang, et al., 2014) or motor cortex will be used as our location of stimulation. To reduce the influence of diurnal variations in the responsiveness to neuroplasticity protocols (Sale, Ridding, & Nordstrom, 2008), we will make every effort to test subjects during the same time of day.

*20-Hz Stimulation (facilitation)* will be delivered at 100% of the motor evoked potential threshold and 20-Hz in trains lasting 2 s for 20 min with 28 second rests in-between trains (similar to Wang et al., 2014).

*Continuous Theta-Burst Stimulation (cTBS; inhibition)* will be delivered at 80% of active motor threshold for 40 seconds (similar to Huang et al., 2005). cTBS consists of 50-Hz triplets separated by 200ms.

*Control stimulation.* As a negative control, rTMS will be delivered to the vertex with the same delivery parameter values and neuronavigation. Wang and colleagues (2014) used vertex stimulation as a control condition and found no significant effects on rsFC or behavior. In addition, there is no evidence that vertex stimulation causes other changes in rsFC (Jung et al., 2016).

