## **10. Statistical Analysis**

### **a. Analysis of data/ study outcomes**

Our primary aim is to examine stimulation-dependent changes in FC within the targeted network in each study. Secondary aims for this protocol will include all behavioral change data from the WPT-F and WPT-O and changes in FC to the non-targeted network, and between networks.

To calculate FC from resting-state scans, the Pearson correlation coefficients ( $r$ ) between time courses of BOLD activity in a seed region (i.e. hippocampus or striatum) will be calculated to determine the FC before and after rTMS stimulation. They will be Fisher-transformed to normalize  $r$ -values.

To calculate FC from task-based scans, the time series from a seed region will be inputted into a general linear model analysis as a regressor along with a regressor indicating when the task is occurring. For the WPT-F, this will include both the choice phase and the feedback phase during learning. For the WPT-O, this will include the observational trials and the retrieval trials. This analysis will be performed on each

individual to create a spatial map of beta values indicating the strength of the association between the seed and other regions during task performance.

*Statistical analysis for Experiments 1 and 3 (targeting the hippocampal network)*

iv. Preliminary Aims

Primary Aim 1

To confirm modulation of the hippocampal network, the average timeseries of the left hippocampal seed will be correlated with all other voxels with available data before and after stimulation. These data will be submitted to AFNI's 3dLME linear mixed effects function, which will be used to reveal potential areas of significant change in rsFC and tbFC.

v. Secondary Aims

Secondary Aims

Behavioral data will be submitted to a 3 x 2 x 2 ANOVA using timepoint (Pre-stimulation, post-stimulation, and follow-up), group (PPC vs. Vertex), and learning type (procedural and declarative) as factors. A significant interaction ( $p < 0.05$ ) between time, group, and learning type will confirm network-dependent modulation of each memory type.

To confirm changes in FC, a similar analysis will be performed as Primary Aim 1, except that the timeseries of the right striatum seed will be used instead of the hippocampal seed.

*Statistical Analysis for Experiments 2 and 4 (targeting the striatal network)*

i. Preliminary Aims

Preliminary Aim 1

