To confirm modulation of the striatal network, the average timeseries of the right striatum seed will be correlated with all other voxels with available data before and after stimulation. These data will be submitted to AFNI's 3dLME linear mixed effects function, which will be used to reveal potential areas of significant change in rsFC and tbFC.

ii. Secondary Aims

Secondary Aims

Behavioral data will be submitted to a 3 x 2 x 2 ANOVA using timepoint (Pre-stimulation, post-stimulation, and follow-up), group (M1 vs. Vertex), and learning type (procedural and declarative) as factors. A significant interaction ( $p < 0.05$ ) between time, group, and learning type will confirm network-dependent modulation of each memory type.

To confirm changes in FC, a similar analysis will be performed as Primary Aim 1, except that the timeseries of the left hippocampus seed will be used instead of the striatal seed.

*Interim Analysis for Experiments 3 and 4.* The data from 3 initial participants in Experiments 3 and 4 will be examined to confirm that cTBS is inhibiting our networks of interest. FC will be calculated within the targeted networks and analyzed by study investigators. If, in the opinion of the study team, inhibition of these networks is unreliable, a cohort of 3 subjects will be run and will receive 1-Hz stimulation instead. Following this cohort, the results will be compared between stimulation protocols and the study team will make an informed decision about whether to continue with cTBS or to switch to 1-Hz stimulation instead.

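### The behavioural interaction planned within each experiment shows a task-specific effect relative to vertex; it cannot confirm that the effect depends on which network was targeted

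*Combined protocol and SAP*

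**What the plan says.** Section 4.a separates the two targets by experiment: "Experiments 1 and 3 will use PPC rTMS. Experiments 2 and 4 will use M1 stimulation". Table 1 pairs Experiments 1 and 2 on 20-Hz stimulation, and 3 and 4 on an inhibitory protocol. In every experiment the comparator is vertex, where "rTMS will be delivered to the vertex with the same delivery parameter values and neuronavigation" (section 4.d, rTMS).

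Under Secondary Aims in section 10.a, "Behavioral data will be submitted to a 3 x 2 x 2 ANOVA using timepoint" together with, for Experiments 1 and 3, "group (PPC vs. Vertex), and learning type (procedural and declarative) as factors". For Experiments 2 and 4 the factors are "group (M1 vs. Vertex), and learning type (procedural and declarative) as factors". Both places then give the same rule: at the 0.05 level, a significant interaction "between time, group, and learning type will confirm network-dependent modulation of each memory type".

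No model in section 10 has target as a factor. The other planned comparisons are the swap of seed region within an experiment, cTBS against 1-Hz, resting against task-based connectivity, and exploratory correlations.

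**The concern.** The three-way interaction asks whether the change from baseline, active minus vertex, differs between WPT-O and WPT-F. The sentence draws two further conclusions from it.

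The first is network dependence. An effect that is absent at vertex, favours one task, and is the same at PPC and M1 would produce the interaction in both experiments, and each would be reported as network-dependent. The data that could show otherwise sit in the paired experiment, and the plan never brings them in.

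The second is modulation of each memory type. A change in one task with none in the other is enough for significance. So is a change opposite to the prediction, because the F test is unsigned. The Précis (Design) does predict directions: in Experiment 1 declarative memory up and procedural learning possibly down, with the inverse expected under inhibition. The decision rule does not use them.

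What is at stake is the wording of a secondary behavioural conclusion. A reader would take it as evidence that stimulating a given network changes that network's own kind of memory.

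**Working it through.** **Inputs from the documents.** There are 13 subjects per group, 26 per experiment and three visits; alpha is 0.05 (sections 10.a, 10.b, Table 2). The only effect and SD given are for connectivity: difference 0.16, pooled SD 0.21 (section 10.b) and pilot t(8) = 2.73 (section 1.b). The plan states no power for the behavioural test, so there is no figure of its own to reproduce.

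**Assumptions.** Both tasks have equal SD and are independent of each other. The correlation between any two visits is ρ. The shift δ (in SDs of one task) is present at both post-stimulation visits. For a central ρ the pilot connectivity figures are borrowed: SD of change = 0.16 × 3 / 2.73 = 0.176, and ρ = 1 − 0.176² / (2 × 0.21²) = 0.65. The range 0.5 to 0.8 is shown around it.

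**Step 1. The planned test.** Let D = WPT-O minus WPT-F at each visit. The three-way interaction is group x time on D. The error variance of D within subjects is 2(1 − ρ). A shift (0, δ, δ), centred over visits, is (−2/3, 1/3, 1/3)δ, with sum of squares 2δ²/3. Split between two groups of n, the interaction sum of squares is n × 2 × ¼ × 2δ²/3 = nδ²/3. Hence

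λ = nδ² / [6(1 − ρ)], with 2 and 48 degrees of freedom.

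For n = 13 and δ = 0.75, λ = 1.219 / (1 − ρ):

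| ρ | λ | P(significant), one experiment |
|---|---|---|
| 0.5 | 2.44 | 25% |
| 0.65 | 3.48 | 35% |
| 0.8 | 6.09 | 56% |

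At ρ = 0.65, δ of 0.25, 0.5 and 1.0 gives 8%, 17% and 57%.

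**Step 2. What the test cannot see.** λ depends on δ², so the sign of δ drops out. A shift of +0.75 at PPC and +0.75 at M1 gives the same rates as +0.75 at PPC and −0.75 at M1. At ρ = 0.65 the chance that at least one of Experiments 1 and 2 is significant is 1 − (1 − 0.347)² = 57% in either case. With no effect at all it is 1 − 0.95² = 10%.

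**Step 3. A term that contains the target.** Pool two experiments (four arms of 13; 2 and 96 degrees of freedom) and test target x group x time x learning type. Results at δ = 0.75, ρ = 0.65:

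| True state | λ | P(significant) |
|---|---|---|
| Same effect at both targets | 0 | 5% |
| Opposite effects at the two targets | 2 × 3.48 = 6.96 | 64% |
| Effect at one target only | 3.48 / 2 = 1.74 | about 20%, against 35% in that experiment alone |

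The last row reflects a standard error √2 = 1.4 times larger, because four arm means enter the contrast instead of two. Simulation of 20,000 pairs of experiments agrees: about 35% per experiment, 57% for at least one, 5% for the same effect at both targets and 64% for opposite effects.

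**Step 4. A limit in the plan's favour.** If stimulation moves both tasks equally, D does not shift and the planned interaction stays at 5%.

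**The case against.** **The tasks are the network markers.** Section 4.d (Behavioral Tasks) ties WPT-F to the caudate and dorsolateral prefrontal cortex, and WPT-O to regions supporting declarative memory. On that reading, network-dependent may only mean that the effect depends on the memory system a task uses, which the interaction does test. This makes the sentence looser rather than false, but it does not rescue the rule, which asks for neither the predicted direction nor an effect on each memory type.

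**The rival effect is narrow.** It must be absent at vertex under the same parameters, alike at PPC and M1, and selective for one task. It must also persist to visits held 12 to 48 hours after the last session and 14 to 21 days after baseline. Passing sensations or arousal during stimulation are not an obvious candidate. This stands: the effect is possible, and nothing in the documents shows it.

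**Connectivity is the plan's evidence on the network.** Section 1.a mentions earlier work showing a "double dissociation between stimulation of different cortical sites and their effects on procedural and declarative memory", and criticises it for lacking a measure of target engagement. That is a remark about other studies, not a claim of this protocol, and it warns that a contrast between sites is not sufficient by itself. This also stands, so a cross-target term has to be read with the connectivity results.

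**Stronger readings a reader might infer.**
- That the study's main conclusion is unsafe. The documents do not support this: behaviour is a secondary outcome (section 9.b), and each primary aim is a connectivity question within one experiment.
- That the planned test has an inflated error rate. It does not. It holds 5% for its own null hypothesis; the fault is in the conclusion drawn.
- That the cross-target term should be the only route to any claim. It loses power if one target fails, and section 10.b says there were no preliminary data for the striatal power calculation.
- That targeted-network connectivity needs the same contrast. It is undefined there, because the seeds and voxelwise maps differ between the paired experiments.

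**Conclusion.** The point holds as a fault of inference in a secondary analysis. A significant interaction in one experiment supports a task-specific effect of that target relative to vertex. It does not support dependence on the targeted network, nor modulation of each memory type. This follows from the structure of the test and needs no numerical assumption.

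The sizes are illustrative. The 25% to 56% per experiment rests on an assumed 0.75 SD shift lasting to both later visits, equal SDs, independent tasks and visit correlations of 0.5 to 0.8, the central value being borrowed from connectivity in nine pilot subjects. Smaller effects give much lower rates. The change is worth making because it is cheap, not because the primary result is at risk.

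**What to change.** In section 10.a, in both Secondary Aims paragraphs:

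1. Replace the confirming sentence. Describe a significant interaction in one experiment as *a task-specific effect of PPC (or M1) stimulation relative to vertex*. Read it in the direction predicted in the Précis, and report the group x time effect for WPT-O and WPT-F separately. The Précis refers only to corresponding behavioural effects for Experiment 2, so write out that direction before the data are seen.

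2. Add one supplementary secondary model for Experiments 1 and 2 with target, group, time and learning type. Cite the four-way term, in the predicted direction, as the evidence that the behavioural effect depends on the target. Do the same for Experiments 3 and 4 only if both end on the same inhibitory protocol; otherwise target and protocol are confounded.

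The cost is a change of wording and one more model per stimulation type, with no new data. State the downsides alongside it:
- The contrast runs across separate experiments, and the documents do not describe how participants are allocated among them. The vertex arms remove overall differences between cohorts, but not differences in response to stimulation.
- It shows dependence on the stimulated site and must be read with the connectivity evidence of target engagement.
- Its standard error is about 1.4 times that of a single experiment, so power is lower if only one target works (about 20% against 35% at 0.75 SD).

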#### Outcome measures

The primary outcome measure is the change in FC produced by rTMS within the targeted network. Between-network FC changes and corresponding memory changes will be secondary outcomes. Exploratory measures will include correlations between individual cognitive differences (questionnaires and NIH Toolbox scores), and our primary and secondary outcome measures.

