### **b. Secondary outcome measures**

- Pre-to-Post rTMS differences in WPT-O scores
- Pre-to-Post rTMS differences in WPT-F scores
- Pre-to-Post rTMS differences in rsFC and tbFC between memory networks.

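### A secondary behavioural interaction at unadjusted p < 0.05 is to count as confirmed network-dependent modulation in each of four experiments, even if the targeted network's connectivity did not change

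*Combined protocol and SAP*

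**What the plan says.** **Behaviour.** Section 10.a, Secondary Aims, has one model per experiment: "Behavioral data will be submitted to a 3 x 2 x 2 ANOVA using timepoint", with stimulation group and learning type as the other factors. The decision rule follows: an interaction at p < 0.05 "between time, group, and learning type will confirm network-dependent modulation of each memory type". It is given for Experiments 1 and 3 (PPC against vertex) and repeated for Experiments 2 and 4 (M1 against vertex).

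**Cross-network FC.** For Experiments 1 and 3 the text reads "To confirm changes in FC, a similar analysis will be performed as Primary Aim 1", with the right striatum as seed. For Experiments 2 and 4 it reads "To confirm changes in FC, a similar analysis will be performed as Primary Aim 1, except that the timeseries of the left hippocampus seed" replaces the striatal one. The analysis referred to is a whole-brain linear mixed-effects map, "which will be used to reveal potential areas of significant change in rsFC and tbFC". No alpha, voxel or cluster threshold, or correction is stated for it.

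**Status of the endpoints.** The Précis says: "Between-network FC changes and corresponding memory changes will be secondary outcomes". Section 9.b lists the two Weather Prediction Task scores and "Pre-to-Post rTMS differences in rsFC and tbFC between memory networks". Section 10.b bases the sample size on the primary outcome alone. Neither section 9 nor section 10 gives a testing order, an alpha split or a multiplicity adjustment.

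**The protocol's own rationale.** Section 1.a sets aside earlier stimulation studies as uninformative about mechanism because they did not measure target engagement. It adopts FC as that measure, and for that reason makes it the primary outcome.

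**The concern.** The behavioural sentence is a decision rule: if the interaction reaches p < 0.05, a claim about networks is confirmed. The test itself contains only behavioural scores. It can show that the learning types changed differently between groups over time. It cannot show that the targeted network was engaged.

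Secondary endpoints are often left unadjusted, which is acceptable when they are presented as support for the primary result. This plan gives one of them confirmatory standing, with neither a link to the primary result nor a statement on multiplicity. What is at stake is the interpretation of the study's distinctive question, namely whether modulating one memory network alters behaviour and connectivity in the other. An isolated p = 0.04 on behaviour could be written up as confirmed modulation in an experiment where the stimulation had no demonstrated effect on its target.

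**Working it through.** The plan states no family-wise error figure, so there is none to reproduce.

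**1. Inputs**
- Alpha for the behavioural interaction: 0.05, one decisive test per experiment (section 10.a).
- Number of experiments: 4, in different participants (Précis, Design; section 4.a). Independence between experiments is therefore a reasonable reading.
- Alpha for cross-network FC: not stated. The number of FC tests is not fixed either. Section 9.b names both resting-state and task-based FC, and section 4.d has two task versions in the scanner.

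**2. From the documented alpha only**
- Per experiment: 0.05. There is no inflation within an experiment.
- At least one false confirmation in four, under the global null: 1 - 0.95^4 = 1 - 0.8145 = 0.1855, or 18.5%. That is 0.1855 / 0.05 = 3.7 times the nominal level.

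**3. Illustration if each FC analysis were a single 0.05-level test (an assumption)**

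With k independent secondary tests per experiment, the rate is 1 - 0.95^k per experiment and 1 - 0.95^(4k) over four.

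| k | Tests counted | Per experiment | Four experiments |
|---|---|---|---|
| 2 | behaviour, one FC analysis | 9.75% | 33.7% |
| 3 | behaviour, resting FC, task FC | 14.3% | 46.0% |
| 4 | behaviour, resting FC, task FC in each task version | 18.5% | 56.0% |

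Tests in the same participants may be correlated, which lowers these figures. Simulating equicorrelated two-sided z-tests (1,000,000 draws) with k = 3 gives 12.6% and 41.5% at correlation 0.5, and 8.4% and 29.5% at correlation 0.9. With k = 2 and correlation 0.9 the figures are 7.0% and 25.2%. In the other direction, a whole-brain map without family-wise correction could have an error rate far above 5%. The documents do not bound this part of the calculation.

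**4. The rule set beside the protocol's rationale**

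| Primary within-network FC effect | Behavioural interaction | Section 10.a concludes | Section 1.a reasoning supports |
|---|---|---|---|
| shown | p < 0.05 | modulation confirmed | behavioural change with evidence of target engagement |
| not shown | p < 0.05 | modulation confirmed | behavioural change, mechanism not shown |

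The two rows get the same conclusion under section 10.a, but section 1.a distinguishes them. This conflict needs no assumption about alpha or test counts.

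**The case against.** The opposing case is substantial.

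- **A reader might infer that about 12 secondary tests run at 0.05, so that 34-46% is the plan's error rate.** The documents do not support this. They attach 0.05 to one behavioural test per experiment. The other eight tests in that count are assumed.
- **A reader might infer that the four experiments must be adjusted together.** Section 2.a gives each experiment its own aim. The experiments differ in site or stimulation type, and no passage claims success if any one of them is positive. Treating them as one family is a judgement, so adjustment across experiments is not required here.
- **A reader might infer that everything outside the section 9.c correlations is confirmatory.** Section 1.d calls the resting-state questionnaire exploratory, and section 4.d.v says the same of the cognitive battery.
- **The behavioural plan already limits multiplicity.** Two tasks over three timepoints are judged by one interaction per experiment. This stands and deserves credit.
- **The verb confirm is used loosely.** It also introduces the primary whole-brain search and the look at three participants in Experiments 3 and 4. For the FC sentences this stands: they state a purpose and carry no decision rule. It does not cover the behavioural sentence, which names a test, a threshold and the conclusion to be drawn.

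The secondary label and the powering on the primary outcome reduce the consequence but do not remove the rule.

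**Conclusion.** The point holds for the behavioural decision rule. In all four experiments a secondary interaction at unadjusted p < 0.05 is to be read as confirming network-dependent modulation, whether or not FC in the targeted network changed. This conflicts with the protocol's own case for measuring target engagement.

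The size that follows from stated alphas is 5% per experiment. The 18.5% over four experiments also requires that they be read as one family, that they be independent and that every null be true. Figures of 10-14% per experiment and 34-46% overall should be quoted only as illustrations, because they further assume two or three independent tests per experiment, each FC analysis being a single 0.05-level test.

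The consequence is for claims and interpretation. It does not touch participant safety or the definition of the primary endpoint. The correction is worth making because it is cheap and limits what the trial may conclude.

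**What to change.** In section 10.a, for both pairs of experiments:

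1. Replace 'will confirm' and 'To confirm' in the Secondary Aims with wording that the results will be taken as supportive evidence.
2. Report estimates with 95% confidence intervals for the behavioural and cross-network FC effects.
3. Describe a behavioural interaction as network-dependent modulation only when that experiment's primary within-network FC effect is also shown. Otherwise report it as a behavioural change.

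Items 1 and 2 are wording changes that need no further data and can be made at once. Item 3 costs more. Section 2.a allows either resting-state or task-based FC to carry the primary aim, and section 10.a gives no threshold, so one primary FC test and its threshold must be defined first. The price in reporting is that an isolated p < 0.05 on a secondary outcome can no longer be presented as confirmation.
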